These clinical studies were carried out in parallel with rodent studies investigating effects of prazosin on alcohol ingestion. Drs. [name] and [name], in collaboration with Drs. [name] and [name] at the Salk Institute, demonstrated that prazosin treatment decreased operant ethanol self-administration by Wistar rats during acute ethanol withdrawal.⁷⁶ In a second study, conducted in collaboration with [name] at the University of Indiana, they demonstrated that both acute and chronic prazosin treatment decreased ethanol consumption by alcohol preferring "P" rats.⁶⁵ In a study evaluating prazosin effects on rewarding properties of alcohol, we demonstrated that prazosin infusion into the ventral tegmentum blocked alcohol-conditioned place preference in mice (manuscript in preparation).

9.4

Objectives/Specific Aims/Research Questions:

Describe the purpose and objective(s) of the study, specific aims, and/or research questions/hypotheses

The objectives of this study are: 1) determine prazosin efficacy for AUD in Service Members (SMs) who are participating in outpatient AUD treatment and 2) determine if the presence of PTSD affects prazosin efficacy for AUD.

The hypotheses are that: 1) prazosin is more effective than placebo for AUD in these SMs; and 2) prazosin effect size will be greater in SMs with PTSD than without PTSD.

Primary outcome measures will consist of the alcohol use calendar and the Penn Alcohol Craving Scale (PACS). Secondary outcome measures will be the Short Inventory of Problems (SIP), and biological markers of alcohol use (phosphatidyl ethanol [PEth] and gamma-glutamyl transferase [GGT]), and successful completion rate of the alcohol treatment program. PTSD symptoms will be assessed with the Clinician Administered PTSD Scale (CAPS) and the PTSD Checklist-Military (PCL-M). Sleep quality will be monitored by the Pittsburgh Sleep Quality Inventory (PSQI). Depression will be assessed by the Patient Health Questionnaire-9 (PHQ-9). Medication compliance will be monitored with pill counts.

9.5 Study Design:

Describe study design in one to two sentences (e.g., prospective, use of existing records/data /specimens, observational, cross-sectional, interventional, randomized, placebo-controlled, cohort, etc.). Specify the phase – Phase I, II, III, or IV – for FDA-regulated investigational drug research

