A blood sample (approx. 10 ml) will be collected at the weeks 8 and 13 for measurement of biological markers of alcohol use (PEth and GGT). GGT measurements will be performed by a Madigan laboratory and results will be placed in the participant's AHLTA record. GGT results will be reported to the participant as clinically indicated and the participant will be referred for medical follow-up, if clinically indicated. PEth samples will be shipped for analysis; however, results will not be available in real time. These results will not be reported to the study participant or to any person not involved in the research.

Study drug adherence will be tracked by pill counts at each study visit.

The blind will be broken at the end of the week 13 visit. Procedures for breaking the blind are described in detail below.

Week 19—6-week follow-up: On week 19 (6 weeks after completion of the week 13 visit), participants will be asked to return for a follow-up visit. At this visit, all outcome assessments (CAPS, alcohol use calendar, PACS, SIP, PSQI, PCL-M, and PHQ-9) will be administered. A blood sample (approx. 10 ml) will be collected for PEth and GGT measurement. Participants will receive a certificate of appreciation at this visit or at the early discontinuation visit as appropriate.

Study personnel will have access to participants' medical records during the period of study participation and for 30 days after study completion or early discontinuation. Records will be reviewed to monitor for changes in health, adverse events, any laboratory results, and completion status of the treatment program. Laboratory results may include urine toxicology screens performed as part of the participant's treatment. Other than the labs listed as being done at screening visit and the GGT that will be obtained at baseline and weeks 8, 13, and 19, no clinical labs will be done as part of the study.

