A unique data element includes any unique features that are not explicitly enumerated in the categories of data in rows 1 – 20 of the table above (in Section 10.10), but that could be used to identify an individual. Unique data elements include characteristics that are not themselves identifying, such as the

rank of general or admiral, or a race or gender, but within the context of other information could be identifiable.

- Yes, I believe there is a reasonable possibility the MHS data will become identifiable
- No, I believe there is no reasonable possibility the MHS data will become identifiable

10.13 HIPAA Privacy Rule and Use of Protected Health Information in Research:

- N/A – will not use or disclose protected health information (PHI)
- HIPAA Authorization will be obtained
- Use of a limited data set where a data use agreement will be obtained
- Waiver/alteration of HIPAA Authorization is being requested

10.14 Managing Data (Data Management and/or Sharing Plan) and/or Human Biological Specimens for this Study:

Include in this section the plan for acquiring data (both electronic and hard copy), access during the study, data/specimen storage and length of time stored, shipment/transmission, and the plan for storage and final disposition at the conclusion of the study. Describe any data agreements in place for accessing data within and/or outside of your institution (e.g., Data Sharing Agreement, Data Use Agreement, Business Agreements, etc.)

Study personnel will have access to participants' medical records during the period of study participation and for 30 days after study completion or early discontinuation. Records will be reviewed to monitor for changes in health, adverse events, any laboratory results, and completion status of the treatment program. Laboratory results may include urine toxicology screens performed as part of the participant's treatment. Other than the labs listed as being done at screening visit and the GGT that will be obtained at baseline and weeks 8, 13, and 19, no clinical labs will be done as part of the study.

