We used these preliminary data to power for both the primary outcome measures, the alcohol use calendar (similar to the Time Line Followback from [name] Voice Response [IVR] Standard Drink Units [SDU] data) and the PACS (from [name] data). Using the SDU data gives us 97% power, 2-tailed at $\alpha=0.05$ with a sample size of 60 in each group (total $N=120$). Using the PACS data gives us 76% power, 2 tailed, at $\alpha=0.05$, and 85% power, one tailed, at $\alpha=0.5$, with the same sample size. We have conservatively powered because [name] used IVR methodology and data were from persons with AUD without PTSD, and [name] were from Service Members with PTSD without diagnosed AUD, to power adequately for not only Hypothesis 1 for prazosin efficacy for AUD, but also Hypothesis 2 to determine the effects of PTSD diagnosis on response to prazosin for treatment of AUD.

Assuming an approximately 40% dropout rate, we will randomize 200 participants to have 120 study completers.

11.3 Total number of subjects requested (including records and specimens):

300

11.4 If you are recruiting by study arm, please identify the arms of the study and how many subjects will be enrolled in each arm

randomize 200 on a 1:1 ratio prazosin or placebo

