Exceptions to confidentiality: The study team will have access to participant medical records from initial consent until 30 days beyond the end of participant study participation to monitor for adverse events and treatment progress. Participant endorsement of illegal substance use, and any self-harm, suicidal or homicidal disclosures will be shared with DBH personnel. Results of the screening labs and GGT testing will be placed in the participants' AHLTA record and will be available to any of the participant's other Army health care providers or any health care providers to whom a participant releases his/her medical records.

14.3

Confidentiality Protections (for research records, data and/or specimens):

Describe in detail the plan to maintain confidentiality of the research data, specimens, and records throughout the study and at its conclusion (e.g., destruction, long term storage, or banking). Explain the plan for securing the data (e.g., use of passwords, encryption, secure servers, firewalls, and other appropriate methods). If data will be shared electronically with other team members/collaborators outside the institution, describe the method of transmission and safeguards to maintain confidentiality. Explain whether this study may collect information that State or Federal law requires to be reported to other officials or ethically requires action, e.g., child or spouse abuse

All study information will be recorded on standardized case report forms (CRFs). CRFs will be labeled with study code number only. Code numbers will be assigned sequentially and will not include participant initials or any other identifiers.

Data will be stored on a secure VA server with restricted access. Only the persons named on the Madigan and VA Puget Sound IRB applications will have access to the source documents and original research data. Data will not be revealed to insurance companies or other individuals or organizations. The code list will be stored on a VA Puget Sound server in a restricted-access folder, which is only accessible by persons named on the protocol. The VA Puget Sound server complies with current Federal standards.

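### Treatment-programme completion is read from records that close 30 days after each participant's own exit, so follow-up for this secondary outcome depends on retention and the arm comparison is at risk of bias if retention differs

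*Combined protocol and SAP*

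**What the plan says.** Section 9.4 lists among the secondary outcomes the "successful completion rate of the alcohol treatment program". No study visit measures it. The source described in 10.1, and repeated in 10.14, is the medical record: "Records will be reviewed to monitor for changes in health, adverse events, any laboratory results, and completion status of the treatment program".

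The access period is given three times, each time counted from the individual's own exit. Section 10.1 has "during the period of study participation and for 30 days after study completion or early discontinuation"; 10.14 repeats it; 14.2 (exceptions to confidentiality) has "from initial consent until 30 days beyond the end of participant study participation". No ascertainment date counted from randomisation is given.

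For someone who stays, 10.1 sets the last contact: "On week 19 (6 weeks after completion of the week 13 visit), participants will be asked to return for a follow-up visit". Section 11.6, however, treats participation as complete at the 13-week visit. On attrition, 11.2 states: "Assuming an approximately 40% dropout rate, we will randomize 200 participants to have 120 study completers".

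Section 11.1 names the secondary outcomes to be analysed, and programme completion is not among them. The plan does not define successful completion, and gives neither a model nor a rule for status still open when access closes.

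**The concern.** A binary outcome that can occur late should be looked for over the same period in both arms. Here the period is fixed by a post-randomisation event, leaving the study, which treatment may influence. Section 13.6 ends participation for those who cannot tolerate a minimum dose, while 11.6 plans to test whether prazosin participants are more likely to complete the medication phase. The plan thus allows for a retention difference in either direction.

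Leaving the study need not mean leaving the programme. Section 13.1 notes that command may require Service Members to finish it, and 14.2 says that a woman discontinued for pregnancy continues customary treatment. Such people can complete the programme after their record window has closed. If their status is then counted as not completed, or dropped, the outcome partly measures study retention. At stake is a misleading comparison on one secondary outcome; the primary outcomes are not affected.

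**Working it through.** **Inputs from the plan.** 200 randomised 1:1, so 100 per arm; about 40% dropout; access to 30 days after exit; last visit at week 19 (10.1), or participation ending at week 13 (11.6).

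**The plan's own figure.** 120 / (1 − 0.40) = 200 randomised, as stated. The implied number of dropouts is 0.40 × 200 = 80.

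**Observation time.** Days observed = exit week × 7 + 30.

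| Exit | Days observed | Share of 163 | Share of 121 |
|---|---|---|---|
| Week 2 | 14 + 30 = 44 | 27% | 36% |
| Week 8 | 56 + 30 = 86 | 53% | 71% |
| Week 12 | 84 + 30 = 114 | 70% | 94% |
| Week 13 | 91 + 30 = 121 | 74% | 100% |
| Week 19 | 133 + 30 = 163 | 100% | n/a |

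**Simple illustration.** Assumptions not in the documents: true completion is 60% in both arms, half of dropouts' completions fall after their window closes, and unresolved status counts as not completed. Observed completion = 0.60 × (1 − 0.5 × dropout).

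- Dropout 45% v 35%: 0.60 × 0.775 = 46.5% v 0.60 × 0.825 = 49.5%, a false difference of 3 points.
- Dropout 50% v 30%: 0.60 × 0.75 = 45% v 0.60 × 0.85 = 51%, a false difference of 6 points.
- Dropout 40% v 40%: 0.60 × 0.80 = 48% in both arms, a false difference of 0.

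**Dependence on programme length.** Further assumptions: dropout times are uniform over weeks 0 to 13, and everyone who completes does so at week T after baseline. The share of dropouts' completions that is captured is p = [13 − (T − 30/7)] / 13, limited to between 0 and 1. For T up to week 23.3 (day 163), observed completion = 0.60 × [(1 − d) + d × p], and the false difference is 0.60 × (difference in dropout) × (1 − p). Rejection rates are for a pooled two-proportion z-test at two-sided 0.05 with 100 per arm and no true effect. Dropout is 30% v 50%.

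| T (week) | p | Observed, 30% dropout | Observed, 50% dropout | False difference (points, unrounded inputs) | Rejection rate |
|---|---|---|---|---|---|
| 4 | 1.00 | 60.0% | 60.0% | 0 | 0.05 |
| 8 | 0.71 | 54.9% | 51.4% | 3.4 | 0.08 |
| 12 | 0.41 | 49.3% | 42.2% | 7.1 | 0.17 |
| 16 | 0.10 | 43.8% | 33.0% | 10.8 | 0.35 |
| 20 | 0 | 42.0% | 30.0% | 12.0 | 0.42 |

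With 35% v 45% dropout the false differences are half as large: 3.6 points at week 12 (rejection rate 0.08) and 5.4 at week 16 (0.12). With equal dropout and equal timing the difference is 0 and the rejection rate 0.05 at every T.

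**Dilution under equal 40% dropout.** Captured share = 0.6 + 0.4p. At week 12 it is 0.763, so a true 60% v 45% difference of 15 points shows as 15 × 0.763 = 11.4. At week 16 it is 0.640, giving 9.6.

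**With one fixed date.** If everyone randomised is ascertained at day 163, capture no longer depends on dropout, and the false difference is 0 in every scenario above.

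**The case against.** A reader might infer that the comparison is biased as the plan stands. The documents do not support that. A false arm difference needs dropout that differs by arm in rate or timing, programmes that end after dropouts' windows close, and unresolved status counted as non-completion or excluded. Section 11.2 gives one overall dropout rate; 11.6 plans to test retention but predicts no difference; programme length is not stated; and no text says how unresolved status is counted. This objection stands.

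Nor does every difference in dropout produce a false difference: a programme ending by about week 4 is fully captured. A longer programme does not always mean more bias either. Once programmes outlast the completers' own window, completers are truncated too, and in the model above the false difference disappears. Recruits are already engaged in treatment (10.1), so the programme clock may start before baseline, which would improve capture.

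Some exits, such as incarceration (13.1) or hospitalisation (13.6), may settle programme status within 30 days. The figure of 80 is not a count of truncated windows, because 11.6 defines completers by visits attended. If participation ends at week 13, late leavers lose little.

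Two possible rescues remain. Section 11.1 anticipates a retrieved-dropout strategy, but describes no procedure and does not link it to record access. Section 10.6 offers contact with health care providers as a data route; the selections cannot be read in the public text, and no ascertainment date is attached to that route. Neither equalises follow-up as written.

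**Conclusion.** The point holds as unequal, retention-dependent ascertainment of a named secondary outcome. That much follows from the text alone: on the week-19 schedule, exits at weeks 2 and 8 are observed for 27% and 53% of a completer's time. Whether this biases the arm comparison is conditional, and its size and direction are unknown. The 3- and 6-point figures, and the 0 to 12 points in the table, are illustrations that rest on assumed completion, dropout by arm, dropout timing and programme length, with unresolved status counted as not completed. With equal dropout and timing there is no false difference, only possible dilution of a true one. The change is worth making because the plan contains nothing that would make the unequal windows harmless, and the remedy is cheap.

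**What to change.** Ascertain programme completion at one fixed time from randomisation for everyone randomised, whatever the date or reason for leaving. Week 19 plus 30 days is a natural choice, since the 10.1 schedule already reaches it for those who stay. Amend the access wording in 10.1, 10.14 and 14.2 and the HIPAA authorisation so that access runs to that date unless the participant withdraws authorisation.

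Define successful completion, add the outcome to the analyses in 11.1, and state how unresolved status is handled. Where access has already ended earlier, report status as undetermined and give sensitivity analyses over plausible values, for example best and worst case by arm. Do not count these participants as non-completers. Do not rely on exclusion or on censoring that assumes non-informative exit, since leaving the study is likely to be related to outcome.

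The cost is protocol and authorisation wording and a few minutes of record review per early leaver, with no added visit or procedure. The downside is somewhat longer record access for people who leave early.

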11.0 Statistical/Data Analysis Plan

11.1 Statistical Considerations:

List the statistical methods to be used to address the primary and secondary objectives, specific aims, and/or research hypotheses. Explain how missing data and outliers will be handled in the analysis. The analysis plan should be consistent with the study objectives. Include any sub-group analyses (e.g., gender or age group). Specify statistical methods and variables for each analysis. Describe how confounding variables will be controlled in the data analysis

Primary Outcome Measures: Analysis of the primary outcomes will follow the ITT principal. For each of the two outcomes, a linear regression model with covariates that include treatment group, the stratifying variables, and baseline value of the outcome will be used to compare the prazosin and placebo groups at 13 weeks. In addition, we will conduct a repeated measures analysis using data from the two points of follow-up (8 and 13 weeks). The repeated measure analysis will be conducted by comparing response profiles between prazosin and placebo groups. An initial comparison will be conducted using the general estimating equations (GEE) method of Liang and Zeger,⁹¹ which allows all observed data points for each participant. Secondarily, an analysis of covariance (ANCOVA) rate of change analysis will be done as a confirmatory or sensitivity analysis. Stratifying variables will be included as covariates in each model since they are factors in the stratification. It is anticipated that a retrieved dropout strategy will

result in a limited number of missing observations. For the GEE analysis no imputation strategy is required. For the ANCOVA analysis the missing data patterns will be evaluated between the treatment groups. If the patterns are similar and the magnitude of missing data is small, a conventional last observation carried forward (LOCF) imputation will be performed. If the amount of missing data is substantial and/or the patterns of missingness disparate, as an alternative to the traditional ANCOVA, the summary statistic method of Dawson⁹² will be employed. This method has been shown to be robust to non-ignorable missingness. The approach summarizes the response profile using a least square slope, and stratifies on the missing data pattern. We will also run analyses to assess the interactions between treatment group and gender.

A completers analyses will be done in a similar fashion for the primary outcome measures, using only the cases that remained on protocol throughout the 13-week study drug period.

Secondary outcome measures: All secondary outcome measures (PSQI, CAPS, PCL-M, SIP, and biological markers) will be analyzed in a manner similar to that described above for the primary outcome measures. (We will also perform exploratory analyses in a similar manner on the CAPS symptom clusters and individual CAPS items to generate hypotheses about differential responsiveness to prazosin for AUD relative to response of individual PTSD symptom clusters/symptoms).

Procedures to minimize missing data: Although all efforts will be made to complete study visits in person, it may be necessary to obtain assessments by telephone. Attempts will be made to reach the participant by telephone. The following actions will be attempted (as appropriate per visit schedule): 1) adverse events will be assessed by telephone, 2) assessments shall be completed by telephone interview with the raters, 3) self-rated measures will be done by mail using prepaid envelopes, and 4) dispensing of study drug shall be done by traceable shipment. No-show, missed visits and actions taken will be documented in the study record.

11.2 Sample Size:

Sample Size Estimation: The power analysis is based on two types of preliminary data: the results of [name] study of prazosin for reduction of alcohol use in persons with AUD without PTSD and the preliminary results of our study of prazosin for combat trauma PTSD in active duty SMs without AUD in which we obtained the PACS. There were 19 completers in [name] pilot study. Standard drink units in the final month of the study drug period were 30.3 ± 32 (mean \pm SD) ($N=10$) in the prazosin group and 62 ± 58 ($N=9$) in the placebo group ($F=1.50$, $p=0.012$). There were 53 completers in the prazosin study for combat trauma PTSD in active duty SMs. The difference (delta) in PACS scores were -2.6 ± 5.8 ($N=27$) vs. -0.3 ± 3.3 ($N=26$) in the prazosin vs. placebo groups, respectively, $t=-1.74$, $p=0.04$ (one-tailed).

We used these preliminary data to power for both the primary outcome measures, the alcohol use calendar (similar to the Time Line Followback from [name] Voice Response [IVR] Standard Drink Units [SDU] data) and the PACS (from [name] data). Using the SDU data gives us 97% power, 2-tailed at $\alpha=0.05$ with a sample size of 60 in each group (total $N=120$). Using the PACS data gives us 76% power, 2 tailed, at $\alpha=0.05$, and 85% power, one tailed, at $\alpha=0.5$, with the same sample size. We have conservatively powered because [name] used IVR methodology and data were from persons with AUD without PTSD, and [name] were from Service Members with PTSD without diagnosed AUD, to power adequately for not only Hypothesis 1 for prazosin efficacy for AUD, but also Hypothesis 2 to determine the effects of PTSD diagnosis on response to prazosin for treatment of AUD.

Assuming an approximately 40% dropout rate, we will randomize 200 participants to have 120 study completers.

11.3 Total number of subjects requested (including records and specimens):

300

11.4 If you are recruiting by study arm, please identify the arms of the study and how many subjects will be enrolled in each arm

randomize 200 on a 1:1 ratio prazosin or placebo

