The titration schedule and target dose were chosen based on clinical experience in treating PTSD with prazosin and on our initial study for AUD in which this titration schedule was well tolerated.¹⁵ Typical, effective, and well-tolerated doses of prazosin in Veterans with PTSD treated at VA Puget Sound range between 5-30 mg/day.⁷⁷ In our prior work with prazosin, study participants have tolerated without difficulty abrupt discontinuation of these doses of prazosin with no need for tapered withdrawal.

Weeks 3-5: If participants delay titration for any reason (e.g., dose maintained and not increased due to temporary AE), the dose may be increased/adjusted through week 5. No dose changes will be allowed after week 5. If titration is required, procedures noted for weeks 1-2 (above) will be followed. If no titration is required, procedures for weeks 6-13 (below) will be followed.

Weeks 6-13: Participants will be asked to return at weeks 6, 7, 8, 9, 11, and 13. At each visit, vital signs, including orthostatic BP and HR, will be measured. Side effects and/or adverse events (if any) will be monitored by open-ended AE reporting and the Adverse Symptom Checklist which includes symptoms which may be attributable to prazosin (e.g., lightheadedness, dizziness on standing, palpitations, drowsiness, headache, nausea, lack of energy, weakness, depressed mood). For vital signs parameters, hypotension will be defined as systolic BP < 90 and clinically meaningful orthostatic hypotension defined as ≥ 20 mmHg drop in systolic BP accompanied by lightheadedness or syncope. If the participant develops an unacceptable adverse effect considered related to study drug, downward dose adjustment will be made.

Concomitant medications and health status will be updated.

The alcohol use calendar will be administered at every study visit. Outcome assessments (CAPS, PCL-M, PHQ-9, PACS, SIP, PSQI) will be administered at weeks 8 and 13.

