Disposition of Data: Case report forms will be stored indefinitely in a locked room accessible only to MIRECC investigators and staff at VA Puget Sound, Seattle division (currently Building 1, Rooms B22 and B25). The Data Managers and Biostatistician will not have access to the link between study code numbers and participant identities. The Project Leader and Study Coordinator will maintain the password-protected link between study code numbers and participant identities. This document will be stored on the VA Research server in a workgroup that is only accessible to approved personnel. The VA Research server is FIPS 140-2 compliant.

Because a Records Retention Schedule approved by National Archives and Records Administration is required to destroy Federal records, and because at this time there is not such a schedule for VA research records, we must retain data pending approval of such a schedule. Therefore, all study data, including the link between participant identities and study code numbers will be maintained until we have permission to destroy them or until data analysis is complete (whichever comes later).

At that time, the code list will be destroyed in compliance with Federal Guidelines in force when the records are destroyed (currently outlined in 44 USC3302§1228.5). The electronic code list will be destroyed in compliance with Federal Guidelines (Currently national Archives and Records Administration rules and National Institute of Standards and Technology 800-88 guidelines for Media Sanitization) and all study data will become anonymous. Anonymous study data will be kept indefinitely.

Description of Assessment Procedures and Instruments:

- *Structured Clinical Interview for DSM-IV Axis I Disorders (SCID):* A widely used structured interview that assesses Axis I psychiatric history. The SCID has very good reliability and validity.⁷⁸⁻⁸⁰ The SCID will be used at the screen visit to rule out exclusionary diagnoses and to describe the participant sample. All parts of the alcohol use disorders section (abuse and dependence) will be asked regardless of answers.
- *Alcohol use calendar:* We will be utilizing a calendar format to obtain self-reports of alcohol use covering the 60-day period prior to Screen and repeated at every visit cover the period since last visit to obtain a retrospective self-report of alcohol use during the study. This will allow for calculation of the number of alcohol positive days, standard

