drink units per day and binge drinking days throughout the trial, which will serve as primary outcome measures.

- *The Penn Alcohol Craving Scale (PACS)*: A self-report paper-and-pencil instrument that assesses various dimensions of craving for alcohol and has been found to have good reliability and validity.⁸¹ The PACS will be administered at baseline and on weeks 8, 13 and 19, and will be used as a primary outcome measure to determine whether prazosin is associated with reductions in alcohol craving.
- *Alcohol Use Disorders Identification Test (AUDIT)*:⁸² A 10-item self-report questionnaire that has served as a screening instrument for alcohol problems in a number of different settings.⁸³ The AUDIT measures at least two factors, one related directly to alcohol consumption and the other to adverse behavioral effects of excessive consumption.^{84, 85} An advantage of the AUDIT is that it can delineate not just individuals likely to have an alcohol use disorder diagnosis but can place respondents on the full spectrum of alcohol misuse from no problem to hazardous drinking to dependence. The AUDIT has well supported reliability, validity, sensitivity, and specificity. The AUDIT will be modified to inquire about the past year, and will be administered at baseline. The AUDIT will be used to characterize the sample.
- *Clinician-Administered PTSD Scale for DSM-IV (CAPS)*:⁸⁶ The 17-item CAPS uses a structured clinical interview designed to assess the 17 symptoms of PTSD outlined in the DSM-IV. The CAPS will be used by the interviewer to make a current (past month DSM-IV diagnoses of PTSD. The frequency and intensity of each symptom on the CAPS is rated on separate 5-point scales, yielding both dichotomous and continuous scores (range = 0 to 8) for each symptom and for the disorder as a whole (range = 0 to 136). The CAPS will be used as a stratification variable for group assignment and as a secondary outcome measure and will be administered at screen, baseline (to be done at baseline only if more than 14 days has elapsed since the screen visit) and weeks 8, 13 and 19.

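### Two primary outcomes in some sections become four in another, the drinking variable and its window are not fixed, and no success rule is set

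*Combined protocol and SAP*

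**What the plan says.** Section 9.4 sets the primary outcomes: "Primary outcome measures will consist of the alcohol use calendar and the Penn Alcohol Craving Scale (PACS"). Section 11.1 keeps that count: "For each of the two outcomes, a linear regression model", adjusted for the stratifying variables and the baseline value, "will be used to compare the prazosin and placebo groups at 13 weeks". It adds "a repeated measures analysis using data from the two points of follow-up (8 and 13 weeks"). Section 11.2 likewise powers two primary measures.

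Section 10.2 differs. Of the calendar it says "This will allow for calculation of the number of alcohol positive days, standard", and the sentence continues "drink units per day and binge drinking days throughout the trial, which will serve as primary outcome measures". The next entry calls the PACS a primary outcome too. That is three plus one.

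On timing, section 10.2 has the calendar cover the 60 days before screening and then be "repeated at every visit cover the period since last visit". Section 10.1 gives the later visits: "Participants will be asked to return at weeks 6, 7, 8, 9, 11, and 13".

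Section 11.2 uses two-sided 0.05 for each outcome with 60 per group (97% power for standard drink units, 76% for the PACS) and adds 85% one-tailed for the PACS with alpha printed as 0.5. No section gives a testing order, a multiplicity adjustment, or a rule for how many primaries must succeed.

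**The concern.** A calendar is an instrument. Until one variable and one look-back period are drawn from it, the first primary analysis is undefined. With three candidate variables and two competing windows, the drinking primary could be settled after data have been seen. Prespecification matters more here because each participant's blind is broken at week 13 or at termination while the trial goes on (10.1, 14.6). The raters stay blind, so this is an opportunity for choice and not a sign of misuse.

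The missing success rule leaves two readings. If one significant primary is enough, the false-positive rate exceeds 5%. If both are needed, it does not, but the power that matters is the joint power, and the plan does not give it.

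A smaller problem follows from the visit spacing. A count of days taken from a single visit's form covers a different length of time at week 8 than at week 13, although 11.1 analyses those two time points together.

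**Working it through.** **1. Reproducing the stated power (11.2).** Inputs: drink units 30.3 (SD 32) against 62 (SD 58); PACS change −2.6 (SD 5.8) against −0.3 (SD 3.3); 60 per group. The standardised effect is d = difference / √((SD₁² + SD₂²)/2).

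- Drink units: 31.7 / √((32² + 58²)/2) = 31.7 / 46.84 = 0.677
- PACS: 2.3 / √((5.8² + 3.3²)/2) = 2.3 / 4.72 = 0.487

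Using the noncentral t with 118 df and noncentrality d√30:

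| Outcome | Test | Computed | Stated |
|---|---|---|---|
| Drink units | two-sided 0.05 | 95.7% | 97% |
| PACS | two-sided 0.05 | 75.4% | 76% |
| PACS | one-sided 0.05 | 84.4% | 85% |
| PACS | one-sided 0.5 | 99.6% | – |

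The stated figures stand. The 85% belongs to alpha 0.05, so the printed 0.5 is wrong.

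**2. Error if any one success counts.** Under independence the rate is 1 − 0.95^k: 9.75% for k = 2 and 18.5% for k = 4. The documents give no correlations, so those below are assumed. The rates come from simulating correlated test statistics, each tested at two-sided 0.05.

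| Outcomes | Assumed correlation | Error |
|---|---|---|
| Two | 0 to 0.7 | 9.8% to 8.3% |
| Four | calendar 0.7, with PACS 0.3 | 15.0% |
| Four | calendar 0.9, with PACS 0.5 | 12.0% |

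**3. Power if both must succeed.** With no correlation, 0.957 × 0.754 = 72.2%. Simulation gives 74.8% at correlation 0.7. Both figures assume the full pilot effects at 60 per arm.

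**4. Windows.** Week 8 − week 7 = 1 week; week 13 − week 11 = 2 weeks. At a constant drinking pattern, a count of drinking days or binge days from the visit form would be about twice as large at week 13 as at week 8. Drink units per day would not change.

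**5. Power under Holm across drink units and PACS** (60 per arm, overall two-sided 0.05).

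| Drinking effect | Drink units | PACS |
|---|---|---|
| Full pilot effect | 93–95% | about 75% |
| Half | not needed here | about 68–70% |
| None | – | about 66–67% |

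In the last row the PACS is in effect tested at 0.025, where its power is 65.5%. In the middle row the t-based value at correlation 0.7 is nearer 67%.

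**The case against.** Section 11.2 powers the calendar with drink-unit data, so the intended drinking measure is signalled. That is fair, but a signal is not a designation: 10.2 names three variables as primary, and the pilot figure is a final-month amount, which is neither of this trial's two stated windows. Section 9.5 also says the study is not meant to support a new indication. That weakens the case for strict family-wise control, but it does not remove the need to say what counts as success.

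Several stronger readings are tempting, and the documents do not support them.

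- A reader might quote 18.5% for four outcomes. That needs zero correlation among three measures taken from the same calendar entries, where every binge day is also a drinking day. It is a limit and not a realistic value.
- A reader might say the drinking outcome doubles between weeks 8 and 13. That holds for day counts from one visit's form. The drink-unit variable in 10.2 is a daily rate, to which it does not apply.
- A reader might count the final month as a third trial window. It describes the pilot data. Because the calendar is completed at every visit, the week 11 and week 13 forms together already cover the last four weeks; only the definition is missing.
- A reader might infer that the trial is underpowered. The stated power reproduces on its disclosed basis of 60 completers per arm.

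**Conclusion.** The concern stands as one of endpoint definition and multiplicity. The sections contradict each other on the number of primaries (two or four) and on the drinking window, the analysed calendar variable is not named, and no success rule exists. One printed alpha is also wrong.

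The size depends on a rule the plan does not state. If any one success counts, the error is about 8–10% for two outcomes (correlation 0.7 to 0) and about 12–15% for four (0.7–0.9 among calendar measures, 0.3–0.5 with the PACS), all correlations assumed. If both must succeed, the error stays within 5% and joint power is about 72–75%, provided both pilot effects hold. These figures leave out any further multiplicity from the GEE and ANCOVA analyses and from the six-monthly interim efficacy reviews.

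**What to change.** - **Variable and window.** In 9.4, 10.2 and 11.1, name one calendar variable as the drinking primary. Drink units per day fits 11.2: dividing a fixed-period total by its number of days leaves d unchanged at 0.677, although that effect was observed over the pilot's final month and need not carry over to another period. State one look-back window and use it for week 8, week 13 and the baseline covariate. Make the other two calendar measures secondary.
- **Success rule.** State Holm at overall two-sided 0.05 across the drinking variable and the PACS. If the investigators keep all four as primary, apply Holm across all four.
- **Typing error.** In 11.2, change the one-tailed alpha from 0.5 to 0.05, or delete that figure.

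This is a change of wording and needs no extra participants. The cost is that two calendar measures lose primary status and power falls somewhat. At 60 per arm, Holm takes about 1–3 points from drink units. It takes about 1 point or less from the PACS if drink units show the full pilot effect, but PACS power falls to about 68–70% at half that effect and about 66–67% at none. The plan should state that dependence, since the drink-unit pilot had only 19 completers.
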